1.3 Study design

This is a randomised, double-blind, placebo-controlled, parallel-group, multicentre, Phase 3 study to evaluate the efficacy and safety of repeat dosing of benralizumab 30 mg administered subcutaneously (SC) versus placebo in patients with severe CRSwNP. Following completion of the double-blind period, patients have the option to enter an OLE.

Approximately 250 patients will be randomised to receive benralizumab 30 mg SC or matching placebo.

Patients will be stratified by region **CCI**

CCI

After enrolment, and prior to screening/run in period (at V1), eligible patients will have their current INCS therapy switched to Mometasone Furoate (400 ug daily) or equivalent (highest local approved for CRSwNP), which should be maintained throughout the study until the last DB visit (V11). Patients must have been on a stable daily dose of INCS for at least 4 weeks prior to V1. Patients will be provided with an electronic patient-reported outcome (ePRO)

device to record symptoms and health-related quality of life (HRQL) data throughout the study until V11 (Week 56).

Patients who continue to meet eligibility criteria will be randomised 1:1 at Visit (V) 3 (Week 0) to receive either placebo or benralizumab 30 mg SC every 4 weeks for the first 3 doses (Weeks 0, 4 and 8) and every 8 weeks (Q8W) thereafter (Weeks 16, 24, 32, 40 and 48). All patients who complete the 56-week DB treatment period on investigational product (IP) may be eligible to continue into an OLE, during which all patients will receive 8 doses of investigational product, every Q4W for the first 3 doses (Weeks 56, 60, 64) and Q8W thereafter (Weeks 72, 80, 88, 96 and 104). Patients randomised to the benralizumab arm during DB period will receive one dose of placebo (dummy) injection at Visit 12 (week 60) in order to not get a loading dose again and to maintain the blind.

During the DB period, patients will return to the study site at dosing visits and at V11 (Week 56) for evaluation of efficacy, safety, PK, ADA, sample collection of blood and nasal secretion for exploratory biomarkers. Patients who enter the OLE period will receive their first OLE dose at V11, after completion of all visit-related assessments. Throughout the OLE period, patients will mainly have assessments related to safety (see [Table 2](#)). The last study visit will occur at 8 weeks after the last dose of IP (Week 112/Follow-up (FU)). Patients who do not enter OLE will have their last study visit at Week 56, end of DB period (EoDB), for follow-up and without administration of IP. If at any point a patient meets IP discontinuation (IPD) criteria, an early IPD visits will be performed. Details about IPD criteria are given in clinical study protocol (CSP), Section 7.1.

Throughout the entire study period, participants will remain on their currently prescribed treatment for CRSwNP.

CT scanning will be performed at V2 (Week -2) and EoDB V11 (Week 56), or IPD if at least 16 weeks since the previous CT scan. In case of surgery during the double-blind part of the study, the CT scan should be done prior to surgery instead of at Week 56 if at least 16 weeks since the previous CT scan. CT scan at V2 will be used both for inclusion criterion (for Asian countries only) and as baseline for efficacy (see CSP, Section 8.1.3).

The primary database lock will occur after all randomised patients have been followed up for the 56-week DB treatment period. The study will remain blinded until the primary database lock. The final database lock will occur after the last patient completes the OLE. All available data captured during the DB treatment period and selected safety data from the OLE period will be analysed at the primary DBL, while remaining data from the OLE period will be reported separately at the final DBL.

1.4 Number of patients

The primary analysis will compare the effect of benralizumab vs placebo on the change from baseline in total NPS at Week 56 and on the change from baseline in bi-weekly mean NBS at Week 56 using a hybrid of worst-possible/worst-observation carried forward and multiple imputation (MI), followed by an analysis of covariance (ANCOVA) with treatment arm,

baseline scores of the corresponding endpoint, region, CCI [REDACTED] as covariates (See Section 4.2.5.1 for details).

Approximately 250 patients will be randomised into SC benralizumab 30 mg or placebo in a 1:1 ratio.

The sample size was estimated based on a 2-sided t-test at a significance level of 0.05. Assuming the population standard deviation (SD) of change from baseline is 2 for total NPS and 1 for NBS, this sample size will provide an overall 80% power to detect a true mean (population) treatment difference of 0.85 units in total NPS and a difference of 0.4 in NBS with a two-sided 0.05 alpha level.

Based on the assumptions above, the minimum observed mean difference of the changes from baseline between benralizumab and placebo that would be statistically significant at the 0.05 level is -0.50 in total NPS and -0.25 in NBS.

2. ANALYSIS SETS

2.1 Definition of analysis sets

Patients must have provided their informed consent. If no signed informed consent is collected (important protocol deviation), then the patient will be excluded from all analysis sets defined below.

2.1.1 All patients analysis set

This analysis set comprises all patients screened for the study and will be used for the reporting of disposition and screening failures.

2.1.2 Full analysis set

All patients randomised and receiving any IP will be included in the FAS, irrespective of their protocol adherence and continued participation in the study. Patients will be analysed according to their randomised treatment. Patients who withdraw consent, and assent when applicable, to participate in the study will be included up to the date of their study termination.

The primary full analysis set (PFAS) consists of all CRSwNP patients with asthma in the FAS.

The summary of demographics will be provided for the PFAS and FAS. Unless otherwise stated, all efficacy analyses will be performed using an Intent-to-treat (ITT) approach based on the PFAS. Efficacy data collected from patients without comorbid asthma at baseline will be listed only.

2.1.3 Safety analysis set

The safety analysis set consists of all patients who have received at least one dose of IP. Patients will be classified according to the treatment they received. A patient who received at least 1 dose of benralizumab will be classified as a patient in the benralizumab treatment group.

Unless otherwise stated, safety and immunogenicity analyses will be conducted based on the safety analysis set, regardless of comorbid asthma status at baseline.

2.1.4 Pharmacokinetic analysis set

All patients who received benralizumab and from whom PK blood samples are assumed not to be affected by factors such as protocol deviations and who had at least one measurable serum PK observation post first dose will be included in the PK analysis dataset.

Pharmacokinetic analyses will be conducted based on the PK analysis set.

2.1.5 OLE analysis set

The OLE analysis set will include all patients who enter the OLE part of the study and who received at least 1 dose of the IP during the OLE treatment period.

Analyses of the OLE period will be conducted based on the OLE analysis set.

2.1.6 Handling of Japan GCP Issue

The Japanese Ministry of Health, Labour and Welfare (MHLW) informed AstraZeneca of an unannounced inspection of a Site Management Organization (SMO). The MHLW identified significant deviations from Good Clinical Practice at the investigator sites supported by the SMO across multiple clinical trials by numerous organisations, including AstraZeneca. To ensure the integrity of clinical trial data, any Japanese patients enrolled from sites managed by the SMO (i.e. study sites **PPD** and **PPD**) will be excluded from all analyses.

- In the disposition table, number of Japanese patients impacted by this issue will be presented in a separate category as “Excluded due to Japan GCP breach” under “Subjects randomised”, and will not be counted in any other category (i.e. completed, withdrawals, etc.).
- All AEs reported by impacted Japanese subjects will be documented in a separate listing.

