9.3. Populations for analyses

For purposes of analysis, the following populations are defined:

Population	Description
All patients analysis set	This analysis set will comprise all patients screened for the study and will be used for reporting of disposition and screening failures.
Full analysis set	All patients randomised and receiving any IP will be included in the FAS, irrespective of their protocol adherence and continued participation in the study. Patients will be analysed according to their randomised treatment. Patients who withdraw consent, and assent when applicable, to participate in the study will be included up to the date of their study termination.
Primary full analysis set	Primary full analysis set consists of all CRSwNP patients with asthma in the FAS.
Safety analysis set	The safety analysis set consists of all patients who have received at least one dose of investigational product. Erroneously treated patients (eg, those randomised to treatment A but actually given treatment B) are accounted for in the treatment group of the treatment they actually received. A patient who has on one or several occasions received IP is classified as active.
Pharmacokinetic analysis set	All patients who received benralizumab and from whom PK blood samples are assumed not to be affected by factors such as protocol violations and who had at least one measurable serum PK observation post first dose will be included in the PK analysis dataset.

OLE analysis set	The OLE analysis set will include all patients who enter the OLE part of the study and who receive at least 1 dose of IP during the OLE treatment period.
------------------	---

Unless otherwise stated, all efficacy analyses will be performed based on the primary full analysis set (PFAS). For consistency, demographic and baseline characteristics will be presented using the PFAS. Safety objectives and the immunogenicity will be analysed based on the safety analysis set. Pharmacokinetic analyses will be conducted based on the PK analysis set.

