6. CHANGES OF ANALYSIS FROM PROTOCOL

Not applicable.

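### Dosed patients at two Japanese sites have their adverse events listed but not tabulated, which departs from the protocol's safety set and is not declared as a change

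*SAP*

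**What the plan says.** SAP 2.1.6 reports that a Japanese ministry inspection found significant GCP deviations at sites supported by a site management organisation (SMO). In response, "any Japanese patients enrolled from sites managed by the SMO", identified as two study sites with redacted numbers, "will be excluded from all analyses". There is no separate rule for safety. Two outputs are specified for these patients:

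- In the disposition table they have one line of their own under the randomised patients and are counted in no other category, so not as completed or withdrawn.
- "All AEs reported by impacted Japanese subjects will be documented in a separate listing".

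The set definitions carry no such exception. Protocol 9.3: "The safety analysis set consists of all patients who have received at least one dose of investigational product". SAP 2.1.3: "The safety analysis set consists of all patients who have received at least one dose of IP". For efficacy, Protocol 9.3 says: "All patients randomised and receiving any IP will be included in the FAS, irrespective of their protocol adherence". Protocol 9.4.2 places the safety analyses on the safety set, and SAP 4.2.10.1 builds the double-blind AE tables on all patients in it.

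SAP 1.1 undertakes to describe any change from the protocol. SAP Section 6, headed "CHANGES OF ANALYSIS FROM PROTOCOL", states that none applies.

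**The concern.** Leaving data from sites with GCP findings out of an efficacy comparison is easy to defend. It is harder to defend leaving serious events in exposed patients out of the safety summaries. Exposure happened whatever the quality of the efficacy records, and the sponsor considers these AEs fit to list.

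A listing shows that an event occurred. It gives no denominator, no rate and no comparison between arms, and 2.1.6 does not say that it will be organised by arm or by study period. The safety conclusion would therefore rest on a subset of the dosed patients. A reader working from the set definitions in the protocol or in SAP 2.1.3 would take the tables to cover everyone dosed.

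**Working it through.** **Reading the rules together**

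| Item | General rule | Effect of SAP 2.1.6 |
|---|---|---|
| Safety set | Everyone with at least one dose (Protocol 9.3, SAP 2.1.3) | Dosed patients of the two sites removed |
| AE, SAE, death and discontinuation tables | All patients in the safety set (SAP 4.2.10.1) | Not in numerator or denominator |
| Crude rate, exposure-adjusted rate, Miettinen-Nurminen risk difference | Built on the treatment groups of those tables | Not included |
| Open-label extension (OLE) AE tables | Everyone with at least one OLE dose (SAP 2.1.5) | Not included |
| Disposition | Completed, discontinued and withdrawn, with reasons (SAP 4.2.1) | One line; no completion or withdrawal count |
| AE records | Summarised and listed | Separate listing only |
| Changes from protocol | To be described (SAP 1.1) | Section 6 declares none |

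A discontinuation for a reason other than an AE is covered neither by the AE listing nor by the disposition counts, and 2.1.6 gives it no other output.

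The SAP amendment history dates the new 2.1.6 to 11 March 2024 and protocol version 5.0 to 6 May 2024. The protocol's version history shows that this later amendment edited Section 9.3. The safety-set definition there still has no site exception.

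**Size**

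The plan gives no figure to reproduce, because the number of affected patients is not stated. Anything numerical is illustration.

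- Scale: the Protocol synopsis gives about 250 patients at about 115 sites. The average is 250 / 115 = 2.17 per site, so 2 × 2.17 = 4.3, or about 4 patients, at two sites.
- Assumed SAE risk per patient, s: 3%, 5% or 10%. The documents give no value.
- Chance that at least one dosed patient with an SAE is missing from the tables: 1 − (1 − s)^n.

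| n dosed at the two sites | Share of 250 | s = 3% | s = 5% | s = 10% |
|---|---|---|---|---|
| 2 | 0.8% | 6% | 10% | 19% |
| 4 | 1.6% | 11% | 19% | 34% |
| 5 | 2.0% | 14% | 23% | 41% |
| 10 | 4.0% | 26% | 40% | 65% |
| 20 | 8.0% | 46% | 64% | 88% |

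Example for n = 4, s = 5%: 1 − 0.95^4 = 1 − 0.815 = 0.185. The expected number of such patients is n × s, from 2 × 0.03 = 0.06 to 20 × 0.10 = 2. The rows for 10 and 20 need sites that enrolled more than twice or four times the average.

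**The case against.** The strongest defence is that 2.1.6 stands beside 2.1.3 under the heading that defines the analysis sets, so it works as a specific exception to a general rule. SAP 2.1 treats patients without signed consent the same way: they are removed from every set without each definition repeating it. Protocol 9.4 leaves the description of the analysed populations to the SAP and sends deviations to the study report. The exclusion is also logged, with its reason, in the SAP amendment history. This stands as far as it goes. A programmer would know what to do and nothing is hidden. But the tables would still cover fewer patients than the protocol's safety set, and Section 6 still says that nothing changed.

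A second defence is that these data may be unreliable, and that full exclusion plus a listing is a reasonable convention. The documents do not say what the inspection found or whether AE records were affected, so the main safety tables need not be forced to include these patients. A labelled supplementary table relies on the data no more than the listing does.

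Three stronger readings are tempting but not supported:

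- *That deaths and SAEs in these patients go unreported.* Every AE goes to the listing, including serious and fatal ones and those leading to discontinuation. The number of patients has its own disposition line, and individual SAE reporting under Protocol 8.4.1 is unaffected.
- *That removing randomised patients biases the comparison.* Whole sites are removed, regardless of arm or outcome, after an external inspection, and the study stays blinded until the primary database lock. The cost is mainly completeness and some precision.
- *That the co-primary analysis must be rerun with these patients.* That would test the result against data from sites where a regulator found significant GCP deviations, and either outcome would be hard to interpret. It is an option, not a requirement.

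**Conclusion.** The point holds as one of incomplete safety tabulation and an undeclared departure from the protocol. Dosed patients of the two sites are listed but not summarised, which departs from the safety set in Protocol 9.3 and SAP 2.1.3, and SAP Section 6 is wrong to declare no change.

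The size is unknown. That these patients were dosed is inferred: 2.1.6 implies that they were randomised but does not say how many received treatment, and anyone never dosed falls outside the safety set anyway. At the trial's average enrolment the numbers are small, about four patients. Nothing in the documents shows that the overall safety conclusion would change. The conflict between the sections does not depend on the assumed figures.

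**What to change.** 1. Keep the exclusion for the efficacy analyses and, if the sponsor wishes, for the main safety tables.
2. In SAP 2.1.6 and 4.2.10.1, add a supplementary overview by arm in all treated patients including the two sites: any AE, SAE, death, and AE leading to discontinuation of investigational product. Provide it for the double-blind and OLE periods, and label it as containing data from sites with GCP findings. Its denominators will show how many treated patients were affected in each arm.
3. State the exception in SAP 2.1.2, 2.1.3 and 2.1.5, with a reference to 2.1.6.
4. Replace the statement in SAP Section 6 with an entry recording the exclusion as a change from the protocol's analysis sets, with the reason.

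The cost is SAP wording and a few extra tables. The drawback is that the tables show data of lower reliability, which is why the label is needed. The primary analysis is unchanged, and no sensitivity analysis of the co-primary endpoints is required.

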2.2 Violations and deviations

Important protocol deviations are a subset of protocol deviations that may significantly impact the completeness, accuracy, and/or reliability of the study data or that may significantly affect a patient’s rights, safety, or well-being.

The final list of important protocol deviations will be documented prior to unblinding the study data, and will include but may not be limited to:

- Inclusion Criteria Deviations
- Exclusion Criteria Deviations
- Discontinuation Criteria for study product met but patient not withdrawn from study treatment
- Discontinuation Criteria for overall study withdrawal met but patient not withdrawn from study
- Investigational Product (IP) Deviation
- Excluded Medications taken
- Deviations to study procedure
- Other Important Deviations

All-important PDs will be identified and documented by the study team prior to unblinding of the trial. Only important protocol deviations will be tabulated in the CSR. Potential important protocol deviations, either programmable or observable, will be reviewed periodically during the trial and at the time of blinded delivery reviews. Additional details for each of the above categories are provided in the Protocol Deviation Plan.

Protocol deviations associated with the COVID-19 pandemic will also be summarised and listed separately (See Section [4.2.11](#)).

3. PRIMARY AND SECONDARY VARIABLES

3.1 General principles

3.1.1 Study periods for data summary

The following study periods will be derived for reporting purposes:

- Double-blind period: this is defined as the period starting on the date of randomization (for efficacy) or date of first dose of study treatment (for safety), and ending on the date of first OLE dose (for those who entered the OLE right after DB completion), or the date of the Week 56 Visit (for those who did not enter the OLE after DB, or those who entered the DB follow-up period per CSP v1.0 and v2.0). For patients who discontinued the study before the Week 56 Visit, the DB period ends on the last participation date.
 - Specifically, patients who enter the OLE period will receive their first OLE dose at the Week 56 Visit, after completion of all visit-related assessments. Therefore, all assessments at the Week 56 Visit are counted under the DB

period, and the first OLE dose (i.e. last procedure at the visit) indicates the start of the OLE period.

- Extended follow-up period, off treatment (applicable to CSP v1.0 or v2.0):
 - for patients who did not enter the OLE: this is defined as the period starting on the date after the end of DB period and ending on the date of last participation in the study.
 - for patients who were followed up off-treatment after DB period and then entered the OLE: this is defined as the period starting on the date after the end of DB period and ending on the date of first OLE dose.
- Open-label period: this is defined as the period starting on the date of first OLE dose and ending on the date of last participation in the study.
- On-study period: this is defined as the period starting on the date of randomization (for efficacy) or date of first dose of study treatment (for safety) and ending on the date of last participation in the study.

3.1.2 Visit window definitions

For endpoints that present visit-based data, the variables will be summarised based on the scheduled days with adjusted analysis-defined visit windows. The adjusted analysis-defined visit windows will be based on the collection schedule listed in the protocol and variables will be windowed to the closest scheduled visit for those variables.

Visit windows have been constructed so that every observation collected can be allocated to a particular visit. However, all values will be included in data listings. Of note, Day 1 indicates the beginning of analysis periods following the Clinical Data Interchange Standards Consortium (CDISC) standards, although it is labelled as Day 0 in the CSP.

For each analysis parameter, the windowing will be based on the protocol-specified schedule of events as defined in Table 1, Table 2, and Table 3 of the CSP. If multiple readings are recorded within a single visit window, the following rules will apply:

- If there are 2 or more valid, non-missing observations within the same visit window, then the non-missing one which is closest to the scheduled visit day will be used in the analysis.
- If 2 valid observations are equidistant from the scheduled visit, then the non-missing observation with the earlier collection date will be used in the analysis for the post-baseline observations and the non-missing observation with the later collection date will be used in the analysis for the screening observations.
- If 2 or more valid observations are collected on the same day after Day 1, then the non-missing observation with the earlier collection time will be included in the

analysis. And the non-missing observation with the later collection time will be included in the analysis if these records were collected during the screening.

- If 2 non-missing values (for continuous variables) are recorded on the same day and have no assessment time associated with at least one of them, or the same assessment time associated with both of them, the average of the two values will be selected for analysis at that visit. For categorical variables in this situation, the worst case will be used.

If a visit window does not contain any observations, then the data will remain missing.

For assignment of data to adjusted analysis-defined visit windows, study day will be calculated relative to the reference start date, which is the date of randomization for efficacy variables and the date of first dose of study treatment for safety variables.

- Screening period: $Study\ day = Date\ of\ assessment - reference\ start\ date$
- After randomisation: $Study\ day = (Date\ of\ assessment - reference\ start\ date) + 1$

The adjusted analysis-defined windows for NPS are defined as in [Table 3](#) below:

Table 3 Adjusted analysis-defined visit windows for NPS

Analysis-defined visit windows	Scheduled study day	Maximum windows
Week -6	-42	$-49 \leq Study\ day \leq -15$
Week -2	-14	$-14 \leq Study\ day \leq 1$
Week 8	57	$2 \leq Study\ day \leq 84$
Week 16	113	$85 \leq Study\ day \leq 140$
Week 24	169	$141 \leq Study\ day \leq 224$
Week 40	281	$225 \leq Study\ day \leq 336$
Week 56	393	$337 \leq Study\ day \leq \min(434, \text{first OLE dose})$; first OLE dose is applicable for those who entered the OLE after DB completion

The NBS, DSS, Total Symptom Score (TSS), and other items in the nasal symptom scores diary (NPSD) will be summarised every two weeks (bi-weekly) and the adjusted windows are defined as in [Table 4](#) below.

Table 4 Adjusted analysis-defined visit windows for NPSD (including NBS, DSS, and TSS)

Analysis-defined visit windows	Scheduled study day	Maximum windows
Week 1, Day 1	1	$-13 \leq Study\ day \leq 1$
Week 2	15	$2 \leq Study\ day \leq 15$
Week 4	29	$16 \leq Study\ day \leq 29$
Week 6	43	$30 \leq Study\ day \leq 43$

...
Week 56	393	$380 \leq \text{Study day} \leq \min(393, \text{first OLE dose})$; first OLE dose is applicable for those who entered the OLE after DB completion

The general adjusted analysis-defined windows for the visits following baseline for all other assessments in Table 2 and Table 3 of the CSP is summarised in Table 5. The windowing will only be performed for assessments within the appropriate periods, e.g. double-blind versus open label.

Table 5 General analysis-defined visit windows for assessments

Analysis-defined visit windows	Scheduled study day	Maximum windows
Week 1 Day 1	1	Study day=1
Week X	$X*7+1=a$	$2 \leq \text{Study day} \leq ((b-a)/2+a)-1$
Week Y ^a	$Y*7+1=b$	$((b-a)/2+a) \leq \text{Study day} \leq ((c-b)/2+b)-1$
Week Z	$Z*7+1=c$	$((c-b)/2+b) \leq \text{Study day}$

[a] For subjects enrolled from CSP v1.0 and v2.0 with efficacy endpoints (SNOT-22, UPSIT, SF-36) collected after Week 56, Week 56 is considered as Week Y in this table.

For visit-based safety summaries during the OLE period: There were 7 subjects who entered the OLE period after being followed up without IP dosing per CSP v1.0 or 2.0. Safety data collected from those subjects during the OLE period are grouped into each timepoint based on the relative duration to the first OLE dose. Specifically, Week 60 is the 2nd scheduled visit (~4 weeks) after the first OLE dose, and Week 64 is the 3rd scheduled visit (~8 weeks) after the first OLE dose, etc.

For local laboratory assessments (including vital signs, ECG), the nominal visit number reported by study sites in web-based data capture (WBDC) will be used in the visit-based summary. Similarly, nominal visit number recorded for scheduled PK assessments in the WBDC will be used for trough concentrations. Unscheduled PK assessments (where nominal visit number is not available) need to be 7-9 weeks (i.e. ± 7 days of Visit X) after the previous IP dosing at Visit X-1 in order to be considered as trough concentration at Visit X.

For overall analyses not based on any particular study visit (e.g. shift tables or event-based analysis), no analysis window will be applied; all data will be listed and/or analysed during analysis periods specified in Section 3.1.1, including any repeat or unscheduled assessments, unless otherwise specified.

